2.2.2 Secondary endpoints

Immunogenicity endpoints

- 1) Geometric Mean Concentration (GMC) and seroconversion rate of anti-gE antibodies 30 days after full immunization;
- 2) Geometric Mean Fold Increase (GMFI) in anti-gE antibodies 30 days after full immunization compared to baseline (Day 0).

Safety endpoints

1. Incidence of solicited adverse events (AE) within 0-7 days after each dose, including local (injection site) and systemic (non-injection site) reactions;
2. Incidence of unsolicited AEs within 0-30 days after each dose;
3. Incidence of AEs within 30 minutes after each dose;
4. Incidence of adverse events of special interest (AESIs) from the first dose through 30 days after full immunization;
5. Incidence of serious adverse events (SAEs) from the first dose through 6 months after full immunization.

3. Study design

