3.1.3.2 Safety observation

Collect all AEs (adverse events) within 30 days after vaccination (including solicited AEs within 30 minutes, 0-7 days, and all unsolicited AEs within 0-30 days). Follow up on all SAEs (serious adverse events) and pregnancy-related events from the first dose of vaccination to 6 months after full immunization.

Solicited AEs include:

Injection site (local) AEs	Pain, pruritus, induration, swelling, rash, redness
Non-injection site (systemic) AEs	Fatigue, tiredness, fever, headache, insomnia, myalgia, skin and mucosal abnormalities, pain at non-injection sites, diarrhea, constipation, vomiting, nausea, acute allergic reactions, arthritis, arthralgia

Unsolicited AEs include: Any adverse event that is not a solicited AE or any solicited AE occurring outside the solicitation period (e.g., If the solicited AEs mentioned above occur more than 7 days after vaccination, they should be recorded as unsolicited AEs). Collection of AESIs (Adverse Events of Special Interest): Suspected cases of herpes zoster within 30 days following the first dose of vaccination to full immunization.

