5.1.7 The second dose of vaccination

The experimental group will receive two dose recombinant zoster vaccine (CHO cells) developed by Beijing Luzhu Biotechnology Co., Ltd./Luzhu Biopharmaceuticals (Zhuhai) Co., Ltd., following a 0 and 30-day immunization schedule.

The control group will receive the two dose Recombinant Zoster Vaccine (RZV, ShingrixTM) developed by GlaxoSmithKline Biologicals SA, following a 0 and 60-day immunization schedule.

Subjects in the experimental group will receive the second dose on Day 30, with a window period of -2/+7 days.

Subjects in the control group will receive the second dose on Day 60, with a window period of -2/+7 days.

If a subject has a relative or absolute contraindication, the vaccination schedule may be postponed or interrupted as described in Section 6.1.1.

Both the experimental and control vaccines will be administered via intramuscular

Group	Study Intervention	Dose	Vaccination Time		
			D0	D30	D60
experimental group	experimental vaccine	0.5mL/dose	√	√	—
control group	control vaccine	0.5mL/dose	√	—	√

injection into the deltoid muscle. The dose and schedule are as follows:

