5.1.9.2 Follow-up Content

The safety observation content includes all adverse events (AEs) and serious adverse events (SAEs) that occur during the study, such as: pain, pruritus, induration, swelling, rash, redness, fatigue, tiredness, fever, headache, myalgia, etc. It also includes the occurrence of all SAEs and pregnancy events from the first dose of vaccination until six months after the full immunization schedule is completed.

Solicited AEs include:

Injection site (local) AEs	Pain, pruritus, induration, swelling, rash, redness
Non-injection site (systemic) AEs	Fatigue, tiredness, fever, headache, insomnia, myalgia, skin and mucosal abnormalities, pain at non-injection sites, diarrhea, constipation, vomiting, nausea, acute allergic reactions, arthritis, arthralgia

Unsolicited AEs include: Any adverse event that is not a solicited AE or any solicited AE occurring outside the solicitation period (e.g., If the solicited AEs mentioned above occur more than 7 days after vaccination, they should be recorded as unsolicited AEs).

Serious Adverse Events (SAEs)

This study will collect all SAEs occurring from the first dose of vaccination until six months after the completion of the full immunization schedule.

Pregnancy Events

All pregnancy events occurring from the first dose of vaccination until six months after the full immunization schedule will be collected. Details on pregnancy reporting, follow-up, and assessment are provided in Section 7.5.

Specially Monitored Adverse Events

Suspected cases of herpes zoster occurring from the first dose of vaccination until 30 days after the completion of the full immunization schedule will be collected.

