7.4.7 Adverse Events of Special Interest (AESIs)

AESIs, specifically suspected cases of herpes zoster, will be collected from the first dose through 30 days after completing the full immunization.

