8.4.4 Safety

This study will primarily focus on the statistical analysis of treatment-emergent adverse events (TEAEs) occurring after vaccination. Adverse events occurring before vaccination will be listed separately. Unless otherwise specified, the term "adverse events" in the following sections refers to TEAEs.

Solicited adverse events occurring 0-7 days post-vaccination, as well as solicited adverse events related to vaccination, will be categorized and analyzed by group, type of reaction (systemic and local), and the severity of each solicited adverse event as listed in Section 3.1.3.2. For these events, the number of adverse events, the number of subjects experiencing them, and the incidence rate will be calculated.

The following adverse events will be categorized and analyzed by group, System Organ Class (SOC), and Preferred Term (PT), calculating the number of events, the number of affected subjects, and the incidence rate:

- Unsolicited adverse events occurring 0-30 days after each dose;
- Adverse events occurring within 30 minutes after each dose;
- All adverse events occurring 0-30 days after each dose;
- Adverse events of special interest occurring from the first dose to 30 days after full immunization;
- Serious adverse events occurring from the first dose to 6 months after full immunization.

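### The synopsis and section 3.1.3.2 state a collection window for suspected herpes zoster (the AESI) that contradicts the endpoint, follow-up, AESI and analysis sections

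*Protocol*

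**What the plan says.** The safety-observation text in Protocol section 3.1.3.2 gives the AESI rule as "Suspected cases of herpes zoster within 30 days following the first dose of vaccination to full immunization". The synopsis repeats the sentence word for word under its own safety-observation heading.

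Elsewhere the window is longer:

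- Section 2.2.2, endpoint: "Incidence of adverse events of special interest (AESIs) from the first dose through 30 days after full immunization". The synopsis endpoint list has the same item.
- Section 5.1.9.2, follow-up content: "Suspected cases of herpes zoster occurring from the first dose of vaccination until 30 days after the completion of the full immunization schedule" are to be collected.
- Section 7.4.7, the AESI section: "AESIs, specifically suspected cases of herpes zoster, will be collected from the first dose through 30 days after completing the full immunization".
- Section 8.4.4, safety analysis: "Adverse events of special interest occurring from the first dose to 30 days after full immunization".

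The length of the window depends on when dose 2 is given, which section 5.1.7 sets by arm: "Subjects in the experimental group will receive the second dose on Day 30, with a window period of -2/+7 days" and "Subjects in the control group will receive the second dose on Day 60, with a window period of -2/+7 days".

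The Schedule of Activities has rows for concomitant medication, pregnancy events and SAEs, and for the Diary and Contact Cards. It has no row for AESIs.

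**The concern.** The odd sentence can end in two places. Either collection stops at full immunization (dose 2), or it stops 30 days after dose 1. Neither reaches the month after dose 2 that the endpoint counts. The synopsis therefore contradicts itself, and section 3.1.3.2 contradicts the endpoint, collection and analysis sections.

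What is at stake is classification more than detection. Under the Definitions of Terms, a suspected case needs only one of three features: unilateral pain or rash, grouped dermatomal vesicles, or neuralgia. Non-injection-site pain and skin or mucosal abnormalities are also on the solicited list, and they become unsolicited events after day 7. A site that believes the AESI window has closed could record the event only under one of those terms, and it would then be missing from the AESI count in section 8.4.4. The six-month SAE follow-up is no backstop, because Appendix 11.2 says that zoster and post-herpetic neuralgia are not SAEs.

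**Working it through.** The protocol gives no AESI window in days, so there is no stated figure to reproduce. The check is arithmetic on the dosing days.

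**Inputs**
- Dose 2 nominally on Day 30 (experimental) and Day 60 (control), each with a -2/+7 day window (section 5.1.7).
- Endpoint window ends 30 days after dose 2 (section 2.2.2).
- All adverse events are collected for 30 days after each dose (section 3.1.3.2). Contact Cards cover days 7 to 30 after each dose (sections 5.1.8 and 5.6).
- Background zoster incidence of 5 per 1000 per year at age 50-59 and 10 per 1000 per year at 60 and over (section 1.1); 150 subjects per arm.

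**Share of the endpoint window cut, with d = day of dose 2**

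Full window = d + 30. Reading A (stop at dose 2) cuts 30/(d + 30). Reading B (stop 30 days after dose 1) cuts d/(d + 30).

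| | Experimental (d = 30) | Control (d = 60) |
|---|---|---|
| Full window | 60 days | 90 days |
| Reading A | 30/60 = 50% | 30/90 = 33% |
| Reading B | 30/60 = 50% | 60/90 = 67% |

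Over the permitted dose-2 window (d = 28 to 37, and d = 58 to 67), reading A gives 45-52% experimental and 31-34% control. Reading B gives 48-55% and 66-69%.

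**Days with neither AESI nor routine adverse-event collection**
- Experimental: Days 0-30 and 30-60 are both covered by the 30-day rule, so there are none under either reading.
- Control, reading A: AESI collection covers Days 0-60 and the rule after dose 2 covers Days 60-90, so there are none.
- Control, reading B: Days 31-59 are uncovered, which is 29 days or about a third of the 90.

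**Expected zoster cases at the section 1.1 rates, 150 × rate × days/365**
- Full window: experimental 150 × 0.005 × 60/365 = 0.12, to 0.25 at the higher rate; control 0.18 to 0.37.
- Days cut: experimental (30 days) 0.06 to 0.12; control 0.06 to 0.12 under reading A (30 days) and 0.12 to 0.25 under reading B (60 days).

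These are rates of zoster. The endpoint counts suspected cases under a broader definition for which the protocol gives no rate, so the figures indicate scale and are not an upper bound.

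**The case against.** The strongest reply is that this is one scrambled sentence set against five clear statements. It contains the same three elements as the endpoint (first dose, 30 days, full immunization) in the wrong order. Each truncating reading has to ignore some of its words: reading A drops the 30 days, and reading B drops full immunization. Sections 5.1.9.2 and 7.4.7 are themselves collection instructions, and section 7.3.3 sends the reader to section 5.1.9 for the timing and content of follow-up. This argument stands. A reader might infer that the protocol does lose a third to two-thirds of the AESI window; the documents do not support that, because the loss occurs only if a site follows the odd sentence against those sections.

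Reading B is also the weaker one. Suspected VZV infection after dose 1 is a criterion for withholding dose 2 (sections 4.4 and 6.1.2), so sites have to look for it through the whole interval between doses, which in the control arm runs to about Day 60.

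A reader might also infer that post-dose-2 cases would go unrecorded or unsampled. Section 3.1.3.2 itself collects all adverse events for 30 days after each dose, and section 3.1.1.2 asks for lesion samples from all suspected cases without a time limit. The inference of arm-dependent bias needs care too: under reading A both arms lose the same 30 days, and the percentages differ only because the full windows are 60 and 90 days by design.

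The contradiction itself remains. The sentence is complete and identical in both places, it does not yield the endpoint window on any literal reading, and the schedule offers no tie-breaker. Recording an event as an ordinary adverse event is not the same as counting it as an AESI.

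**Conclusion.** The contradiction is real: the synopsis safety text and section 3.1.3.2 disagree with the synopsis endpoint list and sections 2.2.2, 5.1.9.2, 7.4.7 and 8.4.4 on when AESI collection ends. The cut of 50% in the experimental arm and 33% (or, less plausibly, 67%) in control assumes nominal dosing days and a site that follows the odd sentence literally. Even then, only control Days 31-59 under reading B would lack routine adverse-event collection; otherwise the effect is cases recorded but not flagged or counted as AESIs.

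This is a minor-to-moderate internal inconsistency, not a design choice. It touches one descriptive secondary safety endpoint and leaves the primary comparison unaffected.

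**What to change.** Reconcile the sentence in the synopsis and in section 3.1.3.2 with the endpoint, follow-up, AESI and analysis sections, so that one AESI data-collection window applies throughout the protocol. Carry that same window into the eCRF and the site instructions.

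The cost is a wording correction in two places plus a check of the eCRF and site materials. No visits are added: Contact Card reviews are already scheduled at Day 60 for the experimental arm and Day 90 for control.

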3.1.4 Study period

Duration of participation for each subject: From the first visit to the last visit, each Study protocol/Version 1.1 /Date: Dec.8, 2023

subject is expected to participate in the study for about 7-8 months.

Duration of the study: From the first visit to the last visit, it is expected to be about 7 to 8 months.

Duration of visit: 6 months after full immunization.

3.2 Rationale for the Selection of the Study Design

3.2.1 Rationale for the Selection of the Control Vaccine

ShingrixTM is a Herpes Zoster subunit vaccine developed by GlaxoSmithKline Biologicals (GSK). The vaccine consists of the VZV glycoprotein E (gE) and a special adjuvant. ShingrixTM in immunocompetent adults ≥ 50 years reduced the incidence of herpes zoster and PHN by 97.2% and 91.2%, respectively, and by 89.8% and 88.8% in elders ≥ 70 years, which showed better efficacy than live attenuated vaccine ZostavaxTM. However, the ultra-high incidence of side effects limits its promising application. In August 2020, this vaccine was officially launched in mainland China for the prevention of herpes zoster in individuals aged 50 and older. The vaccine is administered in a 50 μ g dose via intramuscular injection into the deltoid muscle, with two doses given 1 to 6 months apart.

The herpes zoster subunit vaccine developed by GlaxoSmithKline Biologicals SA (CHO cells) (brand name: ShingrixTM), which is already available on the market in China, has been selected as the active control to evaluate the immunogenicity and safety of the experimental vaccine. The experimental vaccine will follow a 0-30day immunization schedule with two doses, while the control vaccine will follow a 0-60day schedule with two doses. Both the experimental vaccine and the control vaccine will have a dose of 0.5 mL per administration.

3.2.2 Preclinical trial data

3.2.2.1 Comparison of Immunogenicity between LZ901 Vaccine and ShingrixTM Vaccine in BALB/c Mice.

Two weeks after the second immunization, the specific antibody titers (GMT) in mice induced by the LZ901 vaccine and ShingrixTM vaccine were 53.8 and 67.7 times higher, respectively, compared to three weeks after the first dose. The VZV gE GMT for LZ901 and ShingrixTM vaccines were 46,144 and 69,941 ($P > 0.05$), with no significant difference between the two, indicating that the humoral immune response levels induced by the LZ901 and ShingrixTM vaccines are comparable. After immunization with the LZ901 vaccine, mouse lymphocytes stimulated with VZV gE showed that 100% of CD4+ T cells expressed at least two activation markers, and 90% of CD8+ T cells expressed at least two activation markers. Among them, 90% of the gE-specific CD4+ T cells expressed IFN- γ , and 85% of the gE-specific CD8+ T cells expressed CD40L. After immunization with the ShingrixTM vaccine, mouse lymphocytes stimulated with

VZV gE showed that 70% of CD4+ T cells expressed at least two activation markers, and 85% of CD8+ T cells expressed at least two activation markers. Among them, 65% of the gE-specific CD4+ T cells expressed IFN- γ , and 85% of the gE-specific CD8+ T cells expressed CD40L. The expression of other cytokines induced by the LZ901 vaccine was slightly higher than that of the ShingrixTM vaccine. Both the LZ901 and ShingrixTM vaccines induced a Th1-type cell-mediated immune response characterized primarily by the secretion of IFN- γ .

3.2.2.2 Toxicity test of repeated intramuscular injection of LZ901 vaccine for 12 weeks in SD rats with 4 weeks of recovery period

LZ901 vaccine was administered via repeated intramuscular injections to SD rats at doses of 1 dose/rat and 3 doses/rat (50 μ g/dose), with a dosing schedule of once every 3 weeks for a total of 12 weeks (5 doses in total). During the administration period, the main observations included local injection site irritation and immune response related increases in FIB and cytokines IL-2 and IL-6. No significant systemic toxicity reactions were observed, and the no observed adverse effect level (NOAEL) was determined to be 3 doses/rat (50 μ g/dose). At both the 1 dose/rat and 3 doses/rat (50 μ g/dose) levels, local injection site irritation was noted. LZ901 vaccination induced the production of certain levels of VZV gE-specific IgG antibodies and neutralizing antibodies in SD rats, with no signs of immunotoxicity.

3.2.2.3 Active systemic anaphylaxis test of LZ901 vaccine in guinea pigs

No allergic reactions were observed in guinea pigs sensitized by intramuscular injection at the doses of 0.2 and 1 dose/animal (50 μ g/dose), and challenged by intravenous injection at the doses of 0.4 and 2 doses/animal (50 μ g/dose), respectively.

3.2.2.4 Reproductive toxicity study of LZ901 vaccine

This study used a total of 336 SD rats (224 females and 112 males), which were randomly divided into 4 groups by gender (28 males/group; 56 females/group). The groups were as follows: negative control group (administered 0.9% sodium chloride injection), adjuvant control group (administered adjuvant control substance—recombinant zoster vaccine (CHO cells) placebo), low and high dose test groups (administered recombinant zoster vaccine (CHO cells) at doses of 1 dose (50 μ g) per rat and 3 doses (150 μ g) per rat). The vaccine was administered by intramuscular injection in the hind limb, with doses of 0.5 mL per rat and 1.5 mL per rat, respectively. Clinical observations were conducted throughout the study, including checks on the body weight, food intake, and reproductive abilities of the parent female and male rats. At gestation day (GD) 20, cesarean section was performed on female rats to inspect embryonic and fetal development, fetal appearance, bones, and internal organs. After birth, F1 offspring survival, body weight, and physical and reflex development were monitored. Additionally, serum levels of herpes zoster specific IgG antibodies and neutralizing

antibodies in both the GD20 pregnant females, fetal rats, and F1 offspring were measured.

Under the conditions of this study, LZ901 vaccine was administered by intramuscular injection to SD rats before mating, during pregnancy, and through lactation at doses of 1 dose per rat and 3 doses per rat. No significant adverse effects were observed on fertility, pregnancy, and lactation in the parental female and male rats, except for local swelling at the injection site in the 3dose group. No embryotoxicity, teratogenicity, or effects on F1 offspring growth and development were observed. Therefore, the No Observed Adverse Effect Level (NOAEL) for LZ901 vaccine in terms of reproductive toxicity, embryonic and fetal development, and offspring growth and development was determined to be 3 doses per rat. Furthermore, all dose groups of SD rats showed high levels of anti-VZV neutralizing antibodies. Offspring born through normal delivery exhibited higher levels of anti-VZV neutralizing antibodies compared to those born via cesarean section.

3.2.3 Phase I/II Clinical Trial Data

The recombinant zoster vaccine developed by our company has completed Phase I and Phase II clinical trial, evaluating its safety, tolerability, and immunogenicity in healthy individuals aged 50 to 70.

3.2.3.1 Phase I clinical trial

The Phase I clinical trial in healthy individuals aged 50-70 years was conducted with a 0 and 1month immunization schedule, administering one dose of the experimental vaccine or placebo to the deltoid muscle, and a 0 and 2month immunization schedule, administering one dose of the active control vaccine (ShingrixTM) to the deltoid muscle. The trial results showed:

Adverse event rates in the high-dose group, low-dose group, placebo group, and active control group (ShingrixTM) were 30.00%、50.00%、20.00% and 100.00%, respectively.

The adverse event rate in both the experimental vaccine groups was similar to that in the placebo group, but significantly lower than in the active control group. The severity of adverse events was mainly Grade 1, requiring no treatment and resolving spontaneously.

Humoral Immunity: In both high-dose and low-dose groups, the seroconversion rate for anti-gE antibodies (ELISA) 1 month after full immunization was 100%, with antibody levels of 23.73 IU/mL and 24.84 IU/mL, respectively, representing a 16.88 and 34.04fold increase from baseline. The seroconversion rate for anti-VZV antibodies (FAMA) was also 100%, with geometric mean titers (GMT) of 512.00 and 194.01, respectively, reflecting a 36.76 and 13.93fold increase from baseline. The GMT for anti-VZV antibodies was significantly higher in the high-dose group compared to the low-dose group. There were no significant differences between the high-dose, low-dose groups, and the active control group in terms of the seroconversion rate, seroconversion

rate, or 2fold increase in anti-gE and anti-VZV antibodies.

Cellular Immunity: 30 days after full immunization, the proportion of gE-specific CD4+ and CD8+ T cells expressing two or more cytokines (IFN- γ , TNF- α , IL-2, and CD40L) was 85.00%、65.00%、20.00%、75.00%，and 70.00%、55.00%、25.00%、45.00%，and 45.00% in the high-dose, low-dose, placebo, and active control groups, respectively. Both the high-dose and low-dose experimental groups, as well as the active control group, showed significantly higher levels than the placebo group. There were no significant differences between the high-dose, low-dose experimental groups, and the active control group, although the high-dose test group exhibited a slight advantage.

3.2.3.2 Phase II clinical trial

A Phase II clinical trial was conducted in healthy individuals aged 50-70 years to evaluate the immunogenicity and safety of the vaccine. The trial involved administering one dose of the experimental vaccine (either 100 μ g per dose high-dose or 50 μ g per dose low-dose) or placebo to the deltoid muscle at 0 and 30 days, with 150 subjects in each group. The trial results showed:

- Subjects in both the low-dose and high-dose vaccine groups exhibited significantly higher humoral immune responses, including anti-gE and anti-VZV antibodies, compared to the placebo group.
- The seroconversion rates for anti-gE antibodies (ELISA) were 100% in both the high-dose and low-dose vaccine groups one month after the full immunization, and the seroconversion rates for anti-VZV antibodies (FAMA) were 100% in both groups. There were no significant differences between the high-dose and low-dose vaccine groups in terms of seropositivity, seroconversion rates, or the 2fold increase rate.
- One month after full immunization, the anti-gE antibody concentrations in the high-dose and low-dose vaccine groups were 24.19 IU/mL and 16.03 IU/mL, respectively, representing a 21.60fold and 17.42fold increase compared to pre-immunization levels. The geometric mean titer (GMT) for anti-VZV antibodies was 264.77 and 184.90, respectively, representing a 4.98fold and 3.85fold increase. The high-dose group showed significantly higher anti-gE antibody levels ($p<0.0001$) and anti-VZV antibody GMT ($p=0.0017$) compared to the low-dose group, suggesting a potential dose-response relationship.
- The incidence of solicited adverse reactions related to vaccination in the low-dose, high-dose, and placebo groups were 20.00%, 26.85%, and 11.26%, respectively. Both vaccine groups had a higher incidence of adverse reactions than the placebo group, with similar incidence rates between the low-dose and high-dose vaccine groups. The severity of adverse reactions was mostly grade 1, and the reactions were self-alleviating.

In conclusion, the recombinant zoster vaccine demonstrated acceptable safety and

tolerability. The high-dose group (100 μ g per dose) did not show a significant difference in safety compared to the low-dose group (50 μ g per dose); however, the high-dose group exhibited certain advantages in terms of anti-gE antibody levels and cellular immunity. Therefore, the immunization schedule for the Phase III clinical trial of LZ901 will select the 100 μ g per dose recombinant zoster vaccine administered at 0 and 30 days, with two doses in total.

